Cochlear®

Hear now. And always

**CLINICAL INVESTIGATION OF NEW CI DELIVERY MODELS:
STATISTICAL ANALYSIS PLAN**

MAY 30, 2018

Cochlear Americas

[name]
[contact] Toll Free: [name] [contact]
www.Cochlear.com/US

Table of Contents

1	Purpose	3
2	Scope	3
3	Applicable Documents	3
4	Software	3
5	Abbreviations	3
6	Design and Objectives	4
7	Study Variables	4
7.1	Primary Variables	4
7.2	Secondary Variables	4
8	Data Collection	5
9	Sample Size	7
10	Analysis Populations	7
11	Statistical Analyses	7
11.1	Primary Effectiveness Endpoint Analysis Group 1	7
11.2	Primary Effectiveness Endpoint Analysis Group 2	8
11.3	Additional Analysis	8
12	General Statistical Considerations	8
12.1	Descriptive Statistics	8
12.2	Protocol deviations	9
12.3	P-values	9
13	Interim Analyses	9
14	Missing Data Analyses	9
15	Poolability of Data	9
16	Deviations from the Statistical Analysis Plan	9

1 **Purpose**

The purpose of this Statistical Analysis Plan (SAP) is to document analyses that are planned for the Clinical Investigation of New CI Delivery Models before they are performed. The results of the analyses documented here are to be presented in the clinical study final report. Selected analyses may also be presented in interim reports.

2 **Scope**

This SAP should be read in conjunction with the Clinical Study Protocol and Case Report Forms. Changes to the versions of the Clinical Study Protocol (protocol) and Case Report Forms (CRFs) cited above may necessitate updates to the SAP.

3 **Applicable Documents**

Document Number	Document Title
CAM5417 Protocol	Clinical Investigation of New CI Delivery Models in an Nucleus CI Population Version 2.0

4 **Software**

Statistical analyses will be conducted in SAS version 9.3 or above (SAS Institute, Cary, N.C.), R version 3.2 or above (R Core Team, <http://www.R-project.org>) or another validated statistical software package.

5 **Abbreviations**

The following list provides acronyms used in this document and their meaning:

1. AE – adverse event
2. CI – Cochlear Implant
3. CRF – case report form
4. ITT – intent-to-treat
5. PP – per-protocol
6. SAE – serious adverse event
7. SOC – standard of care

6 Design and Objectives

This is a nonrandomized, multi-site, repeated-measures study design to 1) compare the performance in subjects using an expert clinician compared to an Artificial Intelligence MAP on a CNC Monosyllabic Word score and 2) to compare speech recognition. The primary objective is to evaluate the effectiveness of the AI MAP.

The study will contain a minimum of 80 subjects and a maximum of 190 subjects, 30-70 in Group 1 and 50-120 in Group 2.

7 Study Variables

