7.2 Secondary Variables

Additional variables that will be collected and analyzed include clinician satisfaction, subject satisfaction, various psychoacoustic test metrics, AzBio sentences in noise, and CNC monosyllabic phoneme score at 60 dB. The clinician satisfaction, AzBio sentences, CNC monosyllabic words and psychoacoustic test metrics will be collected for both groups of subjects. Subject satisfaction will be collected on the existing subject group only.

8 Data Collection

Table 1 outlines the visits, visit windows, and testing requirements at each evaluation time point for the newly implanted group (Group 1).

Table 1. Follow-up Schedule and Testing Requirements for Newly implanted Subjects

Event	Pre-Operative	Visit A (Initial Activation)	Visit B	Visit C	Visit D
Visit Window	Before implant	2-4 weeks post-surgery	1 month post-Visit A	3 months post-Visit A	6 months post-Visit A
Create AI automaps		√			
Clinical Counseling CNC Words	√	√	√	√ √	√ √
AzBio Sentences in noise				√	√
Program with AI Map			√	√	√
Administer Psychoacoustic Tests (via direct connect):					
Audiogram			√		
Phoneme discrimination			√		
Speech audiometry				√	√
Loudness scaling				√	√
Pending outcome requests (if any)				√	√

Table 2 outlines the visits, visit windows, and testing requirements at each evaluation time point for the existing subjects group (Group 2).

Table 2. Follow-up Schedule and Testing Requirements for Existing Subjects

Event	Visit A	Visit B
Visit Window	NA	1 month post-Visit A
Create AI automaps	√	
CNC Words in sound	√	√
Clinical Counseling	√	√
AzBio Sentences in noise	√	√
Administer Psychoacoustic Tests (via direct connect):		
Audiometry	√	
Phoneme discrimination	√	
Speech audiometry	√	√
Loudness scaling	√	√
Pending outcome requests (if any)		√
Subject Questionnaire		√

9 Sample Size

Sample size for this trial is based upon separate power calculations for the two primary effectiveness endpoints. The study will have a maximum enrollment of 190 subjects with a maximum of 70 newly implanted subjects and a maximum of 120 existing, or previously implanted, subjects.

For the newly implanted subjects (Group 1), analysis will be based on a paired t-test. For a one-sided $\alpha=0.05$ with a standard deviation of 24 and a mean difference between preoperative and 6 month performance as small as 12.7%, at least 80% power will be provided for an evaluable sample size of 30 subjects.

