For the existing subjects (Group 2), analysis will be based on a paired t-test for non-inferiority. For a one-sided $\alpha=0.05$ with a standard deviation of 24 and non-inferiority margin of 10% with no assumed mean difference between AI MAP and EC MAP, at least 90% power will be provided for and evaluable sample size of 50 subjects.

10 Analysis Populations

The Intention-to-Treat (ITT) population will be comprised of all the subjects who are enrolled in the study. All primary analysis will be performed on the ITT population per randomization regardless of the treatment actually received.

11 Statistical Analyses

11.1 Primary Effectiveness Endpoint Analysis Group 1

The statistical analysis of the primary endpoint for Group 1 will be based upon a paired t-test. The hypothesis will compare the improvement of the mean CNC score from the preoperative visit to the 6 month visit by paired t-test. The statistical hypothesis is:

$$H_0: p_t = p_c$$

$$H_a: p_t \neq p_c$$

where p_t is the proportion of subjects with success of the primary endpoint in the treatment arm and p_c is the proportion of subjects with success of the primary endpoint in the control arm. The null hypothesis will be rejected at a 0.05 level.

Table X: Primary Effectiveness Endpoint (Group 1)

	Statistics	Screening	6-Month	Difference
CNC Word Recognition Test	Mean ± SD (N)	13.9 ± 15.2 (31)	60.2 ± 17.2 (31)	46.3 ± 22.0 (31)
	Median (Min, Max)	6.0 (0.0, 58.0)	64.0 (18.0, 85.0)	49.0 (-15.0, 84.0)
	P-value*	N/A	N/A	< 0.001

*P-value for paired difference based on a two-sided, paired t-test with a type I error rate of 5%.

11.2 Primary Effectiveness Endpoint Analysis Group 2

The statistical analysis of the primary endpoint for Group 2 will be based upon a paired t-test for non-inferiority. The hypothesis will compare the mean CNC score from the baseline visit to the 1 month visit by paired t-test for non-inferiority with a margin on 10%. The statistical hypothesis is:

$$H_0: \mu_V \leq \mu_B - M$$

$$H_a: \mu_V > \mu_B - M$$

where μ_V is the mean CNC score at the 1-month visit and μ_B is the mean CNC score at the baseline visit and M is the non-inferiority margin of 10%. The null hypothesis will be rejected at a 0.05 level.

Table X: Primary Effectiveness Endpoint (Group 2)

	Statistics	Baseline	1-Month	Difference
CNC Word Recognition Test	Mean ± SD (N)	60.1 ± 22.8	59.1 ± 22.3	-1.0 ± 10.6 (56)
	Median (Min, Max)	(56) 65.0 (3.0, 90.0)	(56) 62.5 (6.0, 95.0)	-3.5 (-21.0, 49.0)

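### Group 2 power of at least 90% is just missed at 50 evaluable subjects (89.6%; 51 needed), and the Section 6 minimum of 50 leaves no reserve if it counts enrolled subjects

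*SAP*

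**What the plan says.** Section 6 (Design and Objectives) gives the permitted size: "The study will contain a minimum of 80 subjects and a maximum of 190 subjects, 30-70 in Group 1 and 50-120 in Group 2". It does not say whether these are enrolled or evaluable subjects.

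Section 9 (Sample Size) repeats the upper ends of the range as enrolment figures: "The study will have a maximum enrollment of 190 subjects with a maximum of 70 newly implanted subjects", with a cap of 120 for existing subjects. It ties power to evaluable subjects. For Group 1, with SD 24, a difference of 12.7 and a one-sided alpha of 0.05, "at least 80% power will be provided for an evaluable sample size of 30 subjects". For Group 2, with SD 24, a non-inferiority margin of 10, no assumed difference and a one-sided alpha of 0.05, "at least 90% power will be provided for and evaluable sample size of 50 subjects".

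Section 10 says the analysis population "will be comprised of all the subjects who are enrolled in the study". Section 14 analyses the data that are available and names no imputation. For the Group 1 endpoint, Section 11.1 has a two-sided alternative, and its table footnote reads "P-value for paired difference based on a two-sided, paired t-test with a type I error rate of 5".

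**The concern.** The lower ends of the Section 6 range, 30 and 50, are the same numbers that Section 9 requires as evaluable. Because Section 14 uses available data, a subject without both CNC scores drops out of the paired test. If the Section 6 minima count everyone enrolled, a group that stopped at its minimum would meet the planning number only with no loss at all.

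This matters most for Group 2. Its endpoint is a non-inferiority comparison, so too few pairs raise the chance of failing to show non-inferiority when the two MAPs truly perform alike. It is also the group where the stated power has no slack to absorb a loss.

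**Working it through.** **Inputs (Section 9).** Both groups: SD 24, one-sided alpha 0.05, paired t-test. Group 2: margin 10, true difference 0, n = 50. Group 1: difference 12.7, n = 30. The SAP states no loss rate, so 10% and 20% are assumptions.

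**Method.** For n pairs, df = n − 1 and the noncentrality is δ√n/24, where δ is the margin (Group 2) or the difference (Group 1). One-sided power is P(T > t(0.95; df)), with T noncentral t. The two-sided test uses t(0.975; df) and adds the negligible lower tail.

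**Group 2, the stated figure.** At n = 50 the noncentrality is 10 × √50 / 24 = 2.946 and the critical value is 1.677.
- Exact power: 89.6%.
- Normal approximation: Φ(2.946 − 1.645) = Φ(1.301) = 90.3%.

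The stated 90% is therefore reproduced by the approximation and missed by 0.4 points with the named test. At n = 51 the noncentrality is 2.976 and exact power is 90.1%.

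**Group 2, fewer evaluable subjects than 50.**

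| Evaluable | Loss from 50 | Exact power |
|---|---|---|
| 50 | none | 89.6% |
| 49 | one subject | 89.1% |
| 45 | 10% (assumed) | 86.6% |
| 40 | 20% (assumed) | 82.7% |

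**Group 1, both versions of the test.** At n = 30 the noncentrality is 12.7 × √30 / 24 = 2.898.

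| Evaluable | One-sided 0.05 (Section 9) | Two-sided 0.05 (Section 11.1) |
|---|---|---|
| 30 | 88.2% | 80.0% (79.99%) |
| 27 | 84.9% | 75.4% |
| 24 | 80.8% | 70.0% |
| 23 | 79.2% | 67.9% |

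At the one-sided level printed in Section 9, at least 80% holds down to 24 evaluable, so 6 of 30 (20%) could be lost. At the two-sided level, 30 subjects give 80% almost exactly: the difference detectable with 80% power at n = 30 is 12.70, the value that Section 9 prints. This suggests, without proving it, that the Group 1 figure was computed two-sided and labelled one-sided.

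**Room within the caps.** Enrolment needed for 51 evaluable is 51/(1 − loss): 57 at 10% (51/0.9 = 56.7) and 64 at 20% (51/0.8 = 63.8). Both are well below 120.

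**The case against.** **Section 6 does not say enrolled.** It says only what the study will contain, gives no rule for closing a group, and Section 9 applies the word enrolment only to the maxima. The minima can be read as evaluable counts and the maxima as enrolment caps. On that reading the sections agree and the range itself is the loss allowance. This stands as a possible reading. Enrolment remains a fair inference, because Section 9 describes the upper ends of the same range that way, but it is an inference. Clarification is all that can be asked.

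**Loss allowances often sit in the protocol,** which is not at hand. This stands too, so the absence of a dropout rate is not itself the point. The point concerns numbers that the SAP states.

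**A gap of 0.4 points is a difference of method.** It is small and worth one subject. Still, the SAP names a t-test and says at least 90%, and that is not met at 50.

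**The tables in the SAP show paired CNC data on 31 and 56 subjects,** above both planning numbers; at 56 the Group 2 planning power is 92.4%. This stands. The point is about what the wording states and permits, and no shortfall in evaluable numbers is visible in those tables.

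**A stronger reading is tempting:** that the permitted minimum fails to deliver the stated power in both groups. The SAP does not support this for Group 1. The 80% statement is made at one-sided 0.05, where 30 subjects give 88.2%. The shortfall appears only when the two-sided test of Section 11.1 is substituted. That is a conflict between two sections about sidedness, separate from enrolled versus evaluable numbers.

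**Conclusion.** The point holds for Group 2 and is minor. With the named test and Section 9's inputs, 50 evaluable subjects give 89.6% power, and 51 are needed for at least 90%. This part rests on no assumption beyond the SAP's own figures.

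The further fall, to 86.6% or 82.7%, rests on two conditions that the SAP does not settle: that the Section 6 minimum of 50 means enrolled subjects, and that 10% or 20% of them lack a paired score. It should be reported as conditional.

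For Group 1, no shortfall can be claimed on Section 9's terms. Group 1 has no reserve only if the two-sided 5% test of Section 11.1 governs, and the SAP must first settle which test the power statement refers to.

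**What to change.** In Section 6, state the minima as evaluable subjects, defined as those with both paired CNC scores: at least 30 in Group 1 and 51 in Group 2. Adjust the total minimum from 80 to 81 and leave the caps of 70 and 120 unchanged.

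Alternatively, keep 50, say that it means evaluable subjects, and restate the Group 2 power in Section 9 as about 89.6%. If 50 is meant as enrolled, give the power for the evaluable number expected.

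In the same edit, make the Group 1 sidedness agree between Sections 9 and 11.1 and restate the power to match: 88.2% at 30 if one-sided, 80.0% if two-sided. Under the two-sided test, 30 gives 79.99%, so a strict claim of at least 80% would need 31 (81.3%).

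The cost is a few words in the SAP. The enrolment caps stay as they are. The Group 2 evaluable requirement rises by one subject, or its stated power falls by 0.4 points.

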7.1 Primary Variables

There are two primary effectiveness endpoints that will be evaluated within two different groups. The newly implanted group and the existing subjects.

The first primary effectiveness endpoint is the mean improvement of CNC word recognition in quiet at the 6 month time point in comparison to the preoperative baseline score with an appropriately fit hearing aid in the implanted ear. The mean will be collected from the group of newly implanted subjects.

The second primary effectiveness endpoint is the mean CNC word recognition in quiet at the 1 month time point with AI MAP as compared to EC MAP. The mean scores will be collected from the existing subject population.

7.2 Secondary Variables

Additional variables that will be collected and analyzed include clinician satisfaction, subject satisfaction, various psychoacoustic test metrics, AzBio sentences in noise, and CNC monosyllabic phoneme score at 60 dB. The clinician satisfaction, AzBio sentences, CNC monosyllabic words and psychoacoustic test metrics will be collected for both groups of subjects. Subject satisfaction will be collected on the existing subject group only.

8 Data Collection

Table 1 outlines the visits, visit windows, and testing requirements at each evaluation time point for the newly implanted group (Group 1).

Table 1. Follow-up Schedule and Testing Requirements for Newly implanted Subjects

Event	Pre-Operative	Visit A (Initial Activation)	Visit B	Visit C	Visit D
Visit Window	Before implant	2-4 weeks post-surgery	1 month post-Visit A	3 months post-Visit A	6 months post-Visit A
Create AI automaps		√			
Clinical Counseling CNC Words	√	√	√	√ √	√ √
AzBio Sentences in noise				√	√
Program with AI Map			√	√	√
Administer Psychoacoustic Tests (via direct connect):					
Audiogram			√		
Phoneme discrimination			√		
Speech audiometry				√	√
Loudness scaling				√	√
Pending outcome requests (if any)				√	√

Table 2 outlines the visits, visit windows, and testing requirements at each evaluation time point for the existing subjects group (Group 2).

Table 2. Follow-up Schedule and Testing Requirements for Existing Subjects

Event	Visit A	Visit B
Visit Window	NA	1 month post-Visit A
Create AI automaps	√	
CNC Words in sound	√	√
Clinical Counseling	√	√
AzBio Sentences in noise	√	√
Administer Psychoacoustic Tests (via direct connect):		
Audiometry	√	
Phoneme discrimination	√	
Speech audiometry	√	√
Loudness scaling	√	√
Pending outcome requests (if any)		√
Subject Questionnaire		√

9 Sample Size

Sample size for this trial is based upon separate power calculations for the two primary effectiveness endpoints. The study will have a maximum enrollment of 190 subjects with a maximum of 70 newly implanted subjects and a maximum of 120 existing, or previously implanted, subjects.

For the newly implanted subjects (Group 1), analysis will be based on a paired t-test. For a one-sided $\alpha=0.05$ with a standard deviation of 24 and a mean difference between preoperative and 6 month performance as small as 12.7%, at least 80% power will be provided for an evaluable sample size of 30 subjects.

For the existing subjects (Group 2), analysis will be based on a paired t-test for non-inferiority. For a one-sided $\alpha=0.05$ with a standard deviation of 24 and non-inferiority margin of 10% with no assumed mean difference between AI MAP and EC MAP, at least 90% power will be provided for and evaluable sample size of 50 subjects.

10 Analysis Populations

The Intention-to-Treat (ITT) population will be comprised of all the subjects who are enrolled in the study. All primary analysis will be performed on the ITT population per randomization regardless of the treatment actually received.

11 Statistical Analyses

11.1 Primary Effectiveness Endpoint Analysis Group 1

The statistical analysis of the primary endpoint for Group 1 will be based upon a paired t-test. The hypothesis will compare the improvement of the mean CNC score from the preoperative visit to the 6 month visit by paired t-test. The statistical hypothesis is:

$$H_0: p_t = p_c$$

$$H_a: p_t \neq p_c$$

where p_t is the proportion of subjects with success of the primary endpoint in the treatment arm and p_c is the proportion of subjects with success of the primary endpoint in the control arm. The null hypothesis will be rejected at a 0.05 level.

Table X: Primary Effectiveness Endpoint (Group 1)

	Statistics	Screening	6-Month	Difference
CNC Word Recognition Test	Mean ± SD (N)	13.9 ± 15.2 (31)	60.2 ± 17.2 (31)	46.3 ± 22.0 (31)
	Median (Min, Max)	6.0 (0.0, 58.0)	64.0 (18.0, 85.0)	49.0 (-15.0, 84.0)
	P-value*	N/A	N/A	< 0.001

*P-value for paired difference based on a two-sided, paired t-test with a type I error rate of 5%.

11.2 Primary Effectiveness Endpoint Analysis Group 2

The statistical analysis of the primary endpoint for Group 2 will be based upon a paired t-test for non-inferiority. The hypothesis will compare the mean CNC score from the baseline visit to the 1 month visit by paired t-test for non-inferiority with a margin on 10%. The statistical hypothesis is:

$$H_0: \mu_V \leq \mu_B - M$$

$$H_a: \mu_V > \mu_B - M$$

where μ_V is the mean CNC score at the 1-month visit and μ_B is the mean CNC score at the baseline visit and M is the non-inferiority margin of 10%. The null hypothesis will be rejected at a 0.05 level.

Table X: Primary Effectiveness Endpoint (Group 2)

	Statistics	Baseline	1-Month	Difference
CNC Word Recognition Test	Mean ± SD (N)	60.1 ± 22.8	59.1 ± 22.3	-1.0 ± 10.6 (56)
	Median (Min, Max)	(56) 65.0 (3.0, 90.0)	(56) 62.5 (6.0, 95.0)	-3.5 (-21.0, 49.0)
	P-value*	N/A	N/A	< 0.001

*P-value for paired difference based on a one-sided, non-inferiority, paired t-test with a margin of 10% and a type I error rate of 5%.

11.3 Additional Analysis

11.3.1 Analysis of Baseline Characteristics

Table X: Demographic Summary (Group 1)

	Mean \pm SD, Median (Min, Max)
Age at enrollment	63.52 \pm 16.77, 66 (24, 90)
Duration of hearing loss	28.29 \pm 15.92, 26 (3, 56)
	Number and % of subjects
Etiology	
Aging	1 (3.23%)
Genetic	2 (6.45%)
Hereditary	2 (6.45%)
Large Vestibular Aqueduct Syndrome (LVAS)	2 (6.45%)
Meniere's Disease	1 (3.23%)
Meningitis	1 (3.23%)
Noise Exposure	4 (12.90%)
Ototoxic Drugs	1 (3.23%)
Unknown	16 (51.61%)
Ushers 2A	1 (3.23%)
Gender	
Female	15 (48.39%)
Male	16 (51.61%)
Ear Tested	
Left	15 (48.39%)
Right	16 (51.61%)

Table X: Demographic Summary (Group 2)

	Mean \pm SD, Median (Min, Max)
Age at enrollment	56.98 \pm 22.61, 68 (13, 89)
Duration of hearing loss	28.39 \pm 17.92, 25 (1, 74)
Duration of device use (months)	79.30 \pm 75.66, 48 (1, 305)
	Number and % of subjects
Etiology	
Cochlear Malformation	1 (1.79%)
Cytomegalovirus (CMV)	1 (1.79%)
Genetic	8 (14.29%)
Hereditary Presbycusis	1 (1.79%)
High Fever	1 (1.79%)
Large Vestibular Aqueduct Syndrome (LVAS)	3 (5.36%)
Maternal Rubella	1 (1.79%)
Measles	1 (1.79%)
Meniere's Disease	4 (7.14%)
Meningitis	3 (5.36%)
Noise Exposure	4 (7.14%)
Otosclerosis	1 (1.79%)
Unknown	26 (46.43%)
Virus	1 (1.79%)
Type of Sound Processor	
Kanso	1 (1.79%)
N6	49 (87.50%)
N7	6 (10.71%)
Gender	
Female	22 (39.29%)
Male	34 (60.71%)
Ear Tested	
Left	29 (51.79%)
Right	27 (48.21%)

11.3.2 Supportive Efficacy Analyses

Additional summary statistics will be presented for the other auditory tests conducted including:

- AzBio Sentence Tests
- Speech audiometry
- Phoneme discrimination
- Loudness scaling
- Audiometry (using FOX Initial and Standard advice)
- Clinician survey

Table X: Supportive Efficacy Analyses (Group 1)

Variable	Statistic	Result
CNC Word Measure: Screening to 6-Month		
Improvement	n/N (%)	30/31 (96.8%)
	95% Exact CI	(83.3%, 99.9%)
No Change	n/N (%)	0/31 (0.0%)
	95% Exact CI	(0.0%, 11.2%)
Decrement	n/N (%)	1/31 (3.2%)
	95% Exact CI	(0.1%, 16.7%)
AzBio Sentence-in-Noise: 3-Month to 6-Month		
Improvement	n/N (%)	8/31 (25.8%)
	95% Exact CI	(11.9%, 44.6%)
No Change	n/N (%)	16/31 (51.6%)
	95% Exact CI	(33.1%, 69.8%)
Decrement	n/N (%)	7/31 (22.6%)
	95% Exact CI	(9.6%, 41.1%)

Table X: Supportive Efficacy Analyses (Group 2)

Variable	Statistic	Result
CNC Word Measure: Baseline to 1-Month		
Improvement	n/N (%)	4/56 (7.1%)
	95% Exact CI	(2.0%, 17.3%)
No Change	n/N (%)	46/56 (82.1%)
	95% Exact CI	(69.6%, 91.1%)
Decrement	n/N (%)	6/56 (10.7%)
	95% Exact CI	(4.0%, 21.9%)
AzBio Sentence-in-Noise: Baseline to 1-Month		
Improvement	n/N (%)	10/56 (17.9%)
	95% Exact CI	(8.9%, 30.4%)
No Change	n/N (%)	33/56 (58.9%)
	95% Exact CI	(45.0%, 71.9%)
Decrement	n/N (%)	13/56 (23.2%)
	95% Exact CI	(13.0%, 36.4%)

Table X: AzBio Sentences in Noise (Group 1)

	Statistics	3-Month	6-Month	Difference
AzBio Sentence Test	Mean ± SD (N)	39.4 ± 23.0 (31)	42.7 ± 21.5 (31)	3.3 ± 16.7 (31)
	Median (Min, Max)	33.1 (3.6, 84.8)	38.7 (3.6, 76.6)	0.4 (-21.7, 44.2)
	P-value*	N/A	N/A	0.285

*P-value for paired difference based on a two-sided, paired t-test with a type I error rate of 5%.

Table X: AzBio Sentences in Noise (Group 2)

	Statistics	Baseline	1-Month	Difference
AzBio Sentence Test	Mean ± SD (N)	46.7 ± 25.7	46.9 ± 27.4	0.2 ± 15.8 (56)
	Median (Min, Max)	(56) 45.1 (0.7, 96.5)	(56) 47.0 (0.0, 95.7)	-1.4 (-30.8, 61.5)
	P-value*	N/A	N/A	0.907

*P-value for paired difference based on a two-sided, paired t-test with a type I error rate of 5%.

Table X: CNC Monosyllabic Phoneme Score (Group 1)

	Statistics	Screening	6-Month	Difference
CNC Phonemes	Mean ± SD (N)	27.9 ± 23.6 (31)	77.4 ± 12.8 (31)	49.5 ± 26.8 (31)
	Median (Min, Max)	18.7 (0.0, 81.7)	80.3 (39.7, 93.7)	57.7 (-21.3, 91.0)
	P-value*	N/A	N/A	< 0.001

*P-value for paired difference based on a two-sided, paired t-test with a type I error rate of 5%.

Table X: CNC Monosyllabic Phoneme Score (Group 2)

	Statistics	Baseline	1-Month	Difference
CNC Phonemes	Mean ± SD (N)	76.6 ± 17.4 (56)	75.3 ± 17.5 (56)	-1.3 ± 9.3 (56)
	Median (Min, Max)	82.2 (25.3, 96.0)	81.5 (27.7, 97.7)	-1.7 (-22.3, 47.7)
	P-value*	N/A	N/A	0.297

*P-value for paired difference based on a two-sided, paired t-test with a type I error rate of 5%.

Table X: Primary Effectiveness Endpoint by Visit (Group 1)

	Visit	Statistics	Result at Visit	Change from Screening
CNC Word Recognition Test	Screening	Mean \pm SD (N)	13.9 \pm 15.2 (31)	N/A
		Median (Min, Max)	6.0 (0.0, 58.0)	
	3 month	Mean \pm SD (N)	57.3 \pm 17.7 (31)	43.4 \pm 24.1 (31)
		Median (Min, Max)	59.0 (16.0, 86.0)	43.0 (-17.0, 83.0)
		P-value*	N/A	< 0.001
	6 month	Mean \pm SD (N)	60.2 \pm 17.2 (31)	46.3 \pm 22.0 (31)
Median (Min, Max)		64.0 (18.0, 85.0)	49.0 (-15.0, 84.0)	
P-value*		N/A	< 0.001	

*P-value for paired difference based on a two-sided, paired t-test with a type I error rate of 5%.

12 General Statistical Considerations

